## 1 INTRODUCTION

The following Statistical Analysis Plan (SAP) provides the outline for the statistical analysis of the data collected from the ARCT-2303-01 study (protocol version [2.0](#) dated [21 February 2024](#)).

The analyses will be performed sequentially at two different timepoints (Day 57 and end of study). The first final analysis will be conducted at Day 57 and the second final analysis at the end of the study (see Section 10.1 and Section 10.2 for further details).

The planned analyses identified in this SAP may be included in clinical study reports (CSRs), regulatory submissions, or future manuscripts. Also, post hoc exploratory analyses not necessarily identified in this SAP may be performed to further examine study data. Any post hoc, or unplanned, exploratory analyses performed will be clearly identified as such in the final CSR.

Day 57 analysis includes the analyses of immunogenicity (Day 29), reactogenicity (within 7 days post each vaccination), unsolicited adverse events (AEs reported within 28 days post each vaccination), and SAEs, AESIs, MAAEs, and AEs leading to early termination from the study (Day 1 to Day 57). The final study analysis (Day 181) includes the analyses of immunogenicity (Day 181), and SAEs, AESIs, MAAEs, and AEs leading to early termination from the study from Day 1 to Day 181, so the safety analysis will be partially repeated. The database used for the Day 57 analyses will be “frozen” (i.e. soft lock) therefore any potential data modifications that occurs after that date will be reported (e.g. summaries or listings) at the time of the final analyses.

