#### **Cohort A (participants 18 to 64 years of age; N=1200)**

Individuals will be randomly assigned to one of the three study groups:

[figure not shown]
- Group 1a (ARCT-2303/ Flucelvax Quadrivalent, N=400): participants will receive one dose of ARCT-2303 and one dose of Flucelvax Quadrivalent (opposite arms) on Day 1, and one dose of placebo on Day 29.
- Group 2a (ARCT-2303, N=400): participants will receive one dose of ARCT-2303 and one dose of placebo (opposite arms) on Day 1, and one dose of Flucelvax Quadrivalent on Day 29.
- Group 3a (Flucelvax Quadrivalent, N=400): participants will receive one dose of Flucelvax Quadrivalent and one dose of placebo (opposite arms) on Day 1, and one dose of ARCT-2303 on Day 29.

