### 3.8 Treatment Groups

Group 1a: ARCT-2303 + QIV  
Group 2a: ARCT-2303 + Placebo  
Group 3a: QIV + Placebo  
Group 1b: ARCT-2303 + aQIV  
Group 2b: ARCT-2303 + Placebo  
Group 3b: aQIV + Placebo  
ARCT-2303 (Gr 2a and 2b)  
QIV/aQIV (Gr 3a and 3b)  
ARCT-154

If any actual treatments received cannot belong to any one of the treatment groups above (e.g. subject receives only one injection), the participant will be summarized under the randomized treatment group.

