### 3.9 Subgroup Analysis

Subgroup analysis for selected parameters including immunogenicity, solicited AEs, and unsolicited AEs will be performed for the second Final Analysis.

The following subgroups will be assessed for subgroup analysis (last 2 subgroups will be used for immunogenicity data only):

- Gender: Male or Female
- Race: White and Asian
- BMI:  $<30$  and  $\geq 30 \text{ kg/m}^2$
- Country: Australia, Philippines, Costa Rica and Honduras
- Ethnicity: Hispanic or Latino, not Hispanic or Latino
- Vaccine composition of last dose: ancestral, bivalent (BA.1 or BA.5 containing)
- Number of last COVID-19 doses: 3 doses or  $\geq 4$  doses

The descriptive summaries will be presented for subgroup analysis: Groups 2a and 2b combined vs Groups 3a and 3b combined for safety data; Groups 2a and 2b combined for immunogenicity data.

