## 7.2 Unsolicited Adverse Events

All unsolicited AEs including SAEs, MAAEs and AESIs will be coded using MedDRA. Medical occurrences that begin before the study vaccination but after obtaining informed consent will be recorded in the medical history/current medical conditions section of the eCRF, not the AE section, all unsolicited AEs collected on the AE CRF page following the first administration will be considered TEAEs and will be included in the summaries.

Summary tables will include the number of participants (%) experiencing an event along with the number of events. Participants will be counted only once for each SOC and PT level (categorical descriptive analysis). All TEAE summaries will be presented by study group, SOC and PT.

The TEAE summaries will include:

- Overview summary of unsolicited AEs (Day 1 – Day 57)
- Summary of unsolicited AEs reported within 30 minutes after each study vaccination (derived by onset date time if event after vaccination date time) by SOC and PT. Please note that for Day 1, when 2 vaccinations are given, the 30 minutes interval is from the second vaccination.
- Summary of unsolicited AE within 28 days after each study vaccination by SOC and PT.
- Summary of related unsolicited AEs within 28 days after each study vaccination by SOC and PT
- Summary of unsolicited AE within 28 days after each study vaccination by SOC, PT and severity.
- Summary of related unsolicited AEs within 28 days after each study vaccination by SOC, PT and severity
- Summary of SAEs by SOC and PT
- Summary of related SAEs by SOC and PT
- Summary of SAEs by SOC, PT and severity
- Summary of related SAEs by SOC, PT and severity
- Summary of MAAEs by SOC and PT
- Summary of related MAAEs by SOC and PT
- Summary of AESIs by SOC and PT
- Summary of related AESIs by SOC and PT
- Summary of AEs leading to discontinuation from study by SOC and PT
- Summary of related AEs leading to discontinuation from study by SOC and PT
- Summary of (S)AEs with fatal outcome by SOC and PT

Additionally, the following summaries up to 28 days post Day 1 vaccination will be provided for Groups 2a and 2b combined (ARCT-2303), Groups 3a and 3b combined (QIV/aQIV):

- Summary of unsolicited AEs by SOC and PT
- Summary of related unsolicited AEs by SOC and PT
- Summary of SAEs by SOC and PT

For final analysis, summary of SAEs, MAAEs, AESI, AE leading to discontinuation and death will be presented cumulatively (Day 1 to EOS).

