### 10.2 Second Final Analysis

The second final analysis of immunogenicity and safety data collected from Day 57 to the study end will be performed as soon as all data are available. For SAE, MAAE, AESI and AEs leading to discontinuation that will be reported cumulatively (ie from Day 1 to end of study as well). The results of this analysis will be presented in the final CSR. All individual data listings with information on participant study group will be presented in the addendum to the CSR.

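### The cumulative SAE, MAAE, AESI, discontinuation and death tables keep Day 1 treatment labels after Group 3 receives ARCT-2303 on Day 29, so 84% of the follow-up in its column comes after the investigational vaccine

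*SAP*

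**What the plan says.** **Period.** In SAP 7.2 the final-analysis "summary of SAEs, MAAEs, AESI, AE leading to discontinuation and death will be presented cumulatively (Day 1 to EOS"). SAP 10.2 agrees that these events are "reported cumulatively (ie from Day 1 to end of study as well"), and SAP 1 describes the same content as "SAEs, AESIs, MAAEs, and AEs leading to early termination from the study from Day 1 to Day 181". SAP 1 also plans Day 1 to Day 57 versions for the first final analysis.

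**Columns.** SAP 7.2: "All TEAE summaries will be presented by study group, SOC and PT". The labels come from SAP 3.8, for example "Group 3a: QIV + Placebo". Group 3b has the matching label with the adjuvanted vaccine, and the pooled column is "QIV/aQIV (Gr 3a and 3b").

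**Switch.** In Group 3a, SAP 2.1 says "participants will receive one dose of Flucelvax Quadrivalent and one dose of placebo (opposite arms) on Day 1, and one dose of ARCT-2303 on Day" (the day number that completes this sentence is 29). Group 3b follows the same pattern with Fluad. Groups 2a and 2b receive the influenza vaccine on Day 29, and Groups 1a and 1b receive placebo.

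**What is already windowed.** SAP 7.1 tabulates solicited AEs for 7 days after each vaccination. SAP 7.2 tabulates unsolicited and related unsolicited AEs for 28 days after each vaccination. SAP 7.2 also has pooled Group 2 and pooled Group 3 tables limited to 28 days after Day 1, covering unsolicited AEs, related unsolicited AEs and SAEs.

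**Protocol.** Table 10 plans percentages with SAEs, MAAEs and AESIs in the 28 days following each vaccination, as well as overall. SAP 7.2 lists SAE, MAAE and AESI tables without that window, and SAP 9 records no change to the planned analysis.

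**The concern.** After Day 29 every group has been assigned both vaccines, so the labels no longer describe what most of the follow-up represents. An AESI several weeks after a Group 3 participant's ARCT-2303 dose would be tabulated as an event under influenza vaccine plus placebo. A reader comparing Group 2 with Group 3 in the cumulative table would take it as ARCT-2303 against a control without ARCT-2303. That holds only for the first 28 days.

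The safety objective asks about co-administered and standalone use, with SAEs, MAAEs and AESIs followed for 6 months. For MAAEs, AESIs, discontinuations and deaths, no listed table isolates the period in which the randomised groups differ in exposure to ARCT-2303. No listed table counts events from the ARCT-2303 injection onward in everyone who received it.

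Timing matters for cardiac events. Protocol 9.1.14.1 asks participants to report new cardiac symptoms arising up to 6 weeks after each vaccination. For a Day 29 dose that runs to about Day 71 (29 + 42), beyond both the 28-day window and the Day 57 analysis. The only summary table listed for such a late event is the cumulative one.

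**Working it through.** The plan gives no figure for the share of follow-up after the switch, so there is none to reproduce.

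**Inputs**
- Day 29 visit (±3 days) and Day 181 visit (±7 days): SAP 3.1, assessment windows.
- Group sizes: 400 in each of 1a, 2a and 3a; 160 in each of 1b, 2b and 3b (SAP 2.1).
- Planned ARCT-2303 recipients: all 1680, of whom 400 + 160 = 560 (Group 3) are dosed on Day 29 and 1120 on Day 1.

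**1. Share of Group 3 follow-up after ARCT-2303** = (final day − day of second dose) / (final day − 1)
- Nominal: (181 − 29)/(181 − 1) = 152/180 = 84.4%.
- Lowest over the windows: (174 − 32)/(174 − 1) = 142/173 = 82.1%.
- Highest: (188 − 26)/(188 − 1) = 162/187 = 86.6%.
- First final analysis, to Day 57: (57 − 29)/(57 − 1) = 28/56 = 50%.
- If 10% of Group 3 missed the Day 29 dose (assumption): 0.90 × 84.4% = 76.0%. The share falls below half only if about 41% miss it (1 − 0.5/0.844).

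**2. Person-time in Group 3**, full follow-up: 560 × 28/365.25 ≈ 43 person-years before ARCT-2303 and 560 × 152/365.25 ≈ 233 after it.

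**3. Group 3's share of events caused by ARCT-2303**, assuming equal risk and that everyone receives the Day 29 dose
- Short risk window after the dose: 560/1680 = 33.3%.
- Constant excess rate to the end of study: 560 × 152/(560 × 152 + 1120 × 180) = 85,120/286,720 = 29.7%.

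**4. Dilution of the Group 2 to Group 3 rate ratio** (illustration: constant background rate, no effect of the influenza vaccines). If ARCT-2303 multiplies the rate by R from the dose onward, the Day 1 to EOS ratio is R × 180/(28 + R × 152).
- R = 1.5: 270/256 = 1.05.
- R = 2: 360/332 = 1.08, against 2.0 in the first 28 days.
- R = 5: 900/788 = 1.14.
- If R = 2 applies only for 28 days after the dose: Group 2 has 28 × 2 + 152 = 208 units of risk and Group 3 has 28 + 28 × 2 + 124 = 208. The ratio is 1.00, because both groups pass through the same risk window.

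**The case against.** The strongest defence is that the cumulative tables match the stated endpoint. The protocol asks for proportions with SAEs, MAAEs and AESIs over the whole 6 months, and each group is a defined randomised sequence that includes its Day 29 injection. There is no formal safety test. Suspected myocarditis and pericarditis go to expedited reporting and adjudication, the DSMB is unblinded, and the final listings allow each event to be dated against each injection. Protocol Table 10 already plans per-vaccination percentages, and SAP 9 does not withdraw them.

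Much of this stands. The cumulative tables are legitimate if read as sequences, and they should stay. A reader might infer that an ARCT-2303 signal would go unseen. The documents do not support that, because case-level oversight is in place. But listings and adjudication are not tabulated comparisons with denominators, and the SAP 3.8 labels do not tell the reader that the columns are sequences. Table 10 supports the point, because SAP 7.2 does not carry its MAAE and AESI windows forward.

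Three other stronger readings are tempting:
- *All final safety tables are affected.* They are not: solicited and unsolicited AEs are windowed after each vaccination, and SAEs have a pooled pre-switch table.
- *The SAP 3.9 subgroup contrast, "Groups 2a and 2b combined vs Groups 3a and 3b combined for safety data", is contaminated by the switch.* It covers solicited and unsolicited AEs, and wherever SAP 7 defines those pooled groups the window is 7 or 28 days after Day 1. SAP 3.9 states no window, which calls for a clarification only.
- *One third of vaccine-caused events fall under the wrong label.* That is the upper figure, for a short risk window. At a constant rate to the end of study it is about 30%.

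**Conclusion.** The point holds for five event types (SAEs, MAAEs, AESIs, AEs leading to discontinuation, and deaths) in the Day 1 to EOS tables and, with half the Group 3 time after the switch, in the Day 1 to Day 57 versions. Of Group 3's follow-up, 84% (82% to 87% over the visit windows) comes after ARCT-2303 under labels that omit it. This assumes full Day 29 dosing; 10% missed doses would bring the nominal share to 76%. Group 3 would supply about 30% to 33% of events caused by ARCT-2303, given equal risk and full dosing. The dilution ratios are illustrations that depend on the assumed rates.

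The gap is widest for MAAEs, AESIs, discontinuations and deaths, which have no listed pre-switch table. The mismatch between SAP 7.2 and protocol Table 10 is separate and can be seen directly in the text. The consequence is misattribution and dilution in descriptive tables; no error rate, power or primary conclusion is affected. The sponsor's own precedent points the same way: protocol 2.1.2 reports SAEs in the earlier ARCT-154-01 switchover trial separately before and after the switch, by what was then received.

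**What to change.** 1. **SAP 3.8 and 7.2:** keep the cumulative tables, but label columns by the full sequence, for example 'QIV + Placebo, then ARCT-2303'.
2. **SAP 7.2:** for the five event types, add tables split at the Day 29 injection.
   - (a) Day 1 to before that injection, by randomised group. Participants who never receive the Day 29 dose contribute up to their Day 29 visit or withdrawal.
   - (b) Day 29 injection to EOS, by sequence, among those injected. Events after Day 29 in participants not injected are shown separately.
3. **SAP 7.2:** add one table of these events from the ARCT-2303 injection to EOS in all its recipients, with person-time. Use separate columns for co-administered, standalone on Day 1, and Day 29 after influenza vaccine, so that the co-administration question is not blurred by pooling.
4. **SAP 7.2:** restore the per-vaccination 28-day summaries of SAEs, MAAEs and AESIs from protocol Table 10.
5. **SAP 3.9:** state that the pooled Group 2 versus Group 3 safety subgroups use the 7- and 28-day windows after Day 1.

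The cost is SAP and table-shell wording plus a few extra tables. Vaccination date and time (SAP 5.6) and event onset (SAP 7.2) are already collected.

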### **7.3 Vital Signs**

The following vital signs measurements will be taken at the time points specified in the Schedule of Assessments (refer to the Protocol):

- Systolic blood pressure (SBP) (mmHg)
- Diastolic blood pressure (DBP) (mmHg)
- Heart Rate (beats/min);
- Respiratory rate (breaths/min)
- Body Temperature (°C)

All vital signs data collected at scheduled and unscheduled visits will be included in the listings, but only results collected at scheduled visits will be included in the summary tables. Summary tables including results from Day 1, Day 29 and Day 57 will be included in the first analysis and results at Day 181 will be included in the final analysis.

The parameter names that will be used in the outputs will comprise of the test name and the unit of measure, for example, 'Systolic Blood Pressure (mmHg)'. Parameters will be sorted in the order that the measurements were collected in on the Vital Signs eCRF page within the tables and listings.

Vital signs measurements will present summary statistics for the results at the baseline and each scheduled post-baseline visit for each of the parameters. In addition, summaries will be presented for the change from baseline values at each scheduled post-baseline visit (continuous descriptive analysis).

The decimal precision to which the summaries for each parameter will be presented will be based on the maximum number of decimals to which the results were reported on the eCRF.

### **7.4 12-Lead Electrocardiogram (ECG) and Cardiac Enzyme Testing**

A baseline 12-lead ECGs at baseline will be performed for study participants to identify potential asymptomatic myocarditis and pericarditis cases.

In case of suspected myocarditis or pericarditis cases during the study period, detailed evaluation, including ECG, cardiac enzyme testing, and other relevant data should be evaluated.

Additional ECG evaluation at unscheduled visits is at the investigator's discretion.

12-Lead ECG and cardiac enzyme testing results will be presented in the by-participant data listings.

### **7.5 Physical Examinations**

By-participant data listings will be created for all physical examination parameters and all time points.

### **7.6 Pregnancy Test Results**

All information related to pregnancy testing (urine and serum based) will be presented in the by-participant data listings.

### **7.7 Laboratory Assessment SARS-CoV-2**

Results of SARS-CoV-2 rapid antigen testing and any additional SARS-CoV-2 RT-PCR testing will be presented in the by-participant data listings.

### **7.8 Laboratory Assessment Safety**

NA.

## 8 IMMUNOGENICITY

All Immunogenicity analyses will be done using the PP set. For secondary immunogenicity objectives 3, 4, 5 and 6, if more than 5% participants are excluded from PP set as compared to mITT set, then the analysis will be repeated for the mITT analyses set.

Humoral immune responses against Omicron XBB.1.5 subvariant will be assessed by means of Virus Neutralizing assay (VNA) in Groups 1a and 1b, Groups 2a and 2b, and in samples (Days 1 and 29) from ARCT-154 recipients, included in the PPS-1 in study ARCT-154-J01.

Humoral immune responses against QIV and aQIV will be assessed by means of Hemagglutination Inhibition assay (H1N1, H3N2, two B strains, separately) will be assessed in Groups 1a and 1b, and Groups 3a and 3b. In case of lack of agglutination for a specific strain using HI assay, immunogenicity for that strain will be assessed as measured by microneutralization assay as an acceptable alternative.

The per protocol (PP) set will be used for the primary objectives to assess superiority and noninferiority. PPS and PPS1 will be used for primary objectives 1 and 2, whereas PPS will be used for primary objectives 3 and 4.

The GMT ratio for each of the primary immunogenicity endpoints will be assessed by using analysis of covariance (ANCOVA) model that will include covariates and stratification factors (see Section 3.3.2). Two-sided 95% CIs for GMT ratio will be obtained by taking the antilog of the confidence limits for the adjusted mean difference of the logarithmically transformed assay results which is calculated using t-distribution.

Descriptive immunogenicity analysis including GMT, GMFR, and SCR will be produced for each group at all available time points, along with the 95% CIs.

Geometric mean will be calculated as the mean of the antibody results after the data are log-transformed and then taking the antilog of the log-mean to present the results on the original scale. Two-sided 95% CI will be obtained by taking the log transformation of the antibody results and calculated based on t-distribution and then taking the anti-log of the confidence limit. For the calculation of GMT and GMFR, imputation will be applied to antibody titer values above the upper limit of quantitation; ULOQ will be used. Antibody titer values below the lower limit of quantitation will be imputed as  $\frac{1}{2}$  LLOQ (i.e., 0.5\*LLOQ).

GMFR analysis will include participants with antibody results available at both baseline (prior to dose) and post-vaccination. It will be calculated as the mean of the difference after log-transformed results (post baseline minus baseline for each participant) and exponentiating the mean. Two-sided 95% CI will be obtained by taking the log transform of the antibody results and calculating the 95% CI based on t-distribution for the mean difference after the data are log-transformed, then taking the anti-log of the confidence limit. Percentage of participants with seroconversion will be summarized along with the 95% CI by the Clopper-Pearson method (Clopper C, Pearson ES (1934)).

[figure not shown]
Seroconversion is defined as binary variable for participants with non-missing values at pre-vaccination and post-vaccination as:

- = 1, if there is a post-vaccination titer  $\geq 4 \times \text{LLOQ}$  for pre-vaccination titer  $< \text{LLOQ}$
- = 1, if there is at least 4-fold increase (post-vaccination) from pre-vaccination titer  $\geq \text{LLOQ}$
- = 0, otherwise

An alternative SCR is also defined if there is at least a 4-fold increase (post vaccination) from pre-vaccination titer.

### 8.1 Comparison of immune responses

Hypothesis testing will be done in a sequential manner, and all the success criteria at each step need to be met to continue to the next step.

### 8.1.1 Superiority for the Omicron XBB.1.5 subvariant on Day 29 based on GMT

Immunological superiority will be demonstrated by calculating the GMT ratio and the corresponding 95% CI of the SARS-CoV-2 neutralizing antibody titers against Omicron XBB.1.5 subvariant for ARCT-2303 vaccine recipients and ARCT-154-J01 study participants:

$$\text{GMT ratio} = \frac{\text{GMT}_{\text{ARCT-2303}(\text{Groups 2a and 2b})}(\text{Day 29})}{\text{GMT}_{\text{ARCT-154}(\text{booster})}(\text{Day 29})}$$

The analysis of the GMT ratio will be done using ANCOVA, as described in Section 3.3.2. Simple superiority will be concluded if the lower limit of the 2-sided 95% CI for the GMT ratio is higher than 1.0.

### 8.1.2 Noninferiority for the Omicron XBB.1.5 subvariant on Day 29 based on the SCR

SARS-CoV-2 neutralizing antibody seroconversion rates against Omicron XBB.1.5 subvariant for ARCT-2303 vaccine recipients and ARCT-154-J01 study participants will also be compared:

$$\text{SCR difference} = \text{SCR}_{\text{ARCT-2303}(\text{Groups 2a and 2b})} - \text{SCR}_{\text{ARCT-154}(\text{booster})}$$

Seroconversion rate is defined as the percentage of participants with a  $\geq 4$ -fold increase in titer from that at Day 1 (or from LLOQ if Day 1 titer < LLOQ).

The seroconversion rate and its two-sided 95% CI for each group will be calculated using the Clopper-Pearson method. Age group and sex will be applied to calculate the SCR difference based on MH method. Noninferiority will be concluded if the lower limit of the 2-sided 95% CI for SCR difference is higher than - 5% (i.e., minus 5%).

### 8.1.3 Noninferiority for the influenza vaccine strains on Day 29 based on the HI assay

If simple superiority of the GMT and noninferiority of the SCR are concluded in the 2 tests discussed above, immune response for each influenza vaccine strain based on the HI assay

after co-administration of ARCT-2303 and Flucelvax Quadrivalent will be compared to immune response after standalone administration of Flucelvax Quadrivalent

$$\text{GMT ratio} = \frac{\text{GMT}_{\text{QIV+ARCT-2303(Day 29)}}}{\text{GMT}_{\text{QIV+Placebo (Day 29)}}}$$

The analysis of the GMT ratio will be done using ANCOVA, as described in Section 3.3.2. Non-inferiority will be concluded if the lower limit of the 2-sided 95% CI for the GMT ratio is higher than 0.67 for all 4 influenza strains.

